13.4	New York Heart Association (NYHA) Classification	107
13.5	Response Evaluation Criteria for Solid Tumors (RECIST) v1.1	108
13.6	CTCAE v4.03 Grading of Some AEs Relevant to Rovalpituzumab Tesirine	109
13.7	Guidance for Management of Immune-Mediated Adverse Events.....	112
13.8	Paraneoplastic Assessment	120
13.9	Fluid Retention Questionnaire	121
13.10	Adverse Events Expected Due to SCLC or Progression of SCLC	122
13.11	Investigator Signature Page	124
13.12	Document History	125

List of Tables

Table 1.	Planned Cohorts in the Study	21
Table 2.	Study Drug Dosing Schedule	32
Table 3.	Cohort 2 Washout Period Schedule	48
Table 4.	Cohort 3 Washout Period Schedule	48
Table 5.	Recommended Management of Photosensitivity	69

List of Figures

Figure 1.	Study Schema	20
Figure 2.	Adverse Event Collection	58

Definitions of Abbreviations and Terms

ADC	antibody-drug conjugate
AE	adverse event
ALT	alanine aminotransferase
ANA	antinuclear antibodies
ANC	absolute neutrophil count
aPTT	activated partial thromboplastin time
AST	aspartate aminotransferase
AT	aminotransferase
ATA	anti-therapeutic antibody
BA	bioavailability
BE	bioequivalence
β-hCG	beta-human chorionic gonadotropin
BID	twice daily
BSA	Body surface area
BUN	blood urea nitrogen
C _{avgss}	average concentration in steady-state
CBC	complete blood count
CBR	clinical benefit rate
CFR	Code of Federal Regulations
CI	confidence interval
C _{maxss}	steady-state peak concentration
C _{min1}	minimum trough concentration following the first dose
CNS	central nervous system
CR	complete response
CRP	C-reactive protein
CT	computerized tomography
CTA	clinical trial agreement
CTC	circulating tumor cell
CTCAE	Common Terminology Criteria for Adverse Events
CTLA-4	cytotoxic T-lymphocyte antigen 4
cTnT	cardiac troponin T
cTnI	cardiac troponin I
DILI	drug-induced liver injury
DLL3	delta-like protein 3
DLT	dose-limiting toxicity
DOR	duration of response
ECG	electrocardiogram
ECOG	Eastern Cooperative Oncology Group
eCRF	electronic Case Report Form
█	█

eGFR	estimated glomerular filtration rate
EOT	end of treatment
ESR	erythrocyte sedimentation rate
FDA	Food and Drug Administration
GCP	Good Clinical Practice
HBcAb	Hepatitis B core antibody
HBsAb	Hepatitis B surface antibody
HBsAg	Hepatitis B surface antigen
HCV	Hepatitis C virus
IB	Investigator's Brochure
ICF	Informed consent form
ICH	International Conference on Harmonization
IEC	Independent Ethics Committee
IHC	Immunohistochemistry
IHR	infusion or hypersensitivity reaction
IL	Interleukin
INR	international normalized ratio
IRB	Institutional Review Board
IV	intravenous(ly)
LDH	lactate dehydrogenase
LTFU	long-term follow-up
LVEF	left ventricular ejection fraction
MRI	magnetic resonance imaging
MTD	maximum tolerated dose
NCI	National Cancer Institute
NET	neuroendocrine tumor
NSCLC	Non-small cell lung cancer
NSE	neuron-specific enolase
NYHA	New York Heart Association
ORR	objective response rate
OS	overall survival
PBD	pyrrolbenzodiazepine
PBMC	peripheral blood mononuclear cells
PCR	polymerase chain reaction
PD	progressive disease
PD	pharmacodynamic
PD-1	programmed death receptor-1
PD-L1	anti-PD-L1 antibody
PD-L2	Anti-PD-L2 antibody
PET	positron emission tomography
PFS	progression-free survival

PK	Pharmacokinetic(s)
PO	per os (by mouth/orally)
PPK	population pharmacokinetics
PR	partial response
PT	prothrombin time
PTT	partial thromboplastin time
q2wk	every 2 weeks
q3wk	every 3 weeks
q4wk	every 4 weeks
q6wk	every 6 weeks
q12wk	every 12 weeks
QA	quality assurance
QTc	QT interval corrected for heart rate
QTcF	QT interval corrected for heart rate by Fridericia's formula
RBC	red blood cell
RCC	Renal cell carcinoma
RECIST	Response Evaluation Criteria in Solid Tumors
RF	rheumatoid factor
RP2D	recommended phase 2 dose
SAE	serious adverse event
SCLC	small cell lung cancer
SD	stable disease
SMC	safety monitoring committee
SPF	sun protection factor
TEAE	treatment-emergent adverse event
TPC	tumor perpetuating cells
ULN	upper limit of normal
USP	United States Pharmacopeia

1. Introduction

1.1 Small Cell Lung Cancer (SCLC)

Small cell lung cancer (SCLC) is an important unmet medical need, representing 15–20% of the 220,000 annual new cases of lung cancer (Govindan, 2006; Siegel, 2012). These cancers arise from epithelial cells with neuroendocrine differentiation and typically are positive for both cytokeratin and neuroendocrine markers; however, the diagnosis is usually made by morphologic examination. Historically, SCLC has been divided into limited versus extensive-stage disease, the former being defined as disease limited to the chest that can be encompassed by a radiation field while the latter includes all other cases. Approximately one-third of newly diagnosed patients will have limited-stage disease while the rest will be extensive. Unlike non-small cell lung cancer (NSCLC), SCLC is rarely cured with local therapy (surgery and/or radiotherapy); systemic chemotherapy remains the cornerstone of therapy for all stages of disease. Standard initial therapy for all patients with a suitable performance status consists of a platinum salt (carboplatin or cisplatin) in combination with a second agent, usually etoposide. For patients with limited-stage disease, concurrent or sequential involved-field thoracic radiotherapy is indicated. Response rates to initial therapy are high, ranging from 70-90% for limited stage and 60–70% for extensive-stage; however, recurrence rates remain high in the limited group and universal in the extensive group, leading to median survivals of only 14-20 months and 9-11 months, respectively (Simon, 2004).

1.2 Delta-like Protein 3 and Rovalpituzumab Tesirine

Delta-like protein 3 (DLL3) is an inhibitory ligand of the Notch receptor family. It is highly expressed in high-grade tumors of neuroendocrine origin such as SCLC, including its tumor perpetuating cells (TPCs), but with no detectable surface protein expression in normal tissues or non-neuroendocrine tumor (NET) types (Saunders, 2015; AbbVie data on file). While the function of DLL3 has not been clearly defined, it has been implicated in the regulation of cell development and fate decisions (Dunwoodie, 1997; Chapman, 2011).

Rovalpituzumab tesirine (SC16LD6.5) is a DLL3-targeted antibody-drug conjugate (ADC) consisting of the humanized DLL3-specific IgG1 monoclonal antibody SC16; the DNA cross-linking agent SC-DR002 (D6.5); and a protease-cleavable linker that covalently links SC-DR002 to SC16. The primary mechanism of rovalpituzumab tesirine is binding of the ADC to DLL3 on target-expressing cells, followed by internalization of the ADC-DLL3 complex and release of SC-DR002 via proteolytic cleavage in late endosomes. Interstrand crosslinks of cellular DNA induced by intercalated SC-DR002 leads to cellular cytotoxicity.

In a Phase 1 study (SCRX16-001), rovalpituzumab tesirine exhibited encouraging efficacy in recurrent SCLC, achieving a 31% (8/26) and 85% (22/26) central review-adjudicated confirmed objective response rate (ORR) and clinical benefit rate (CBR) (39% [10/26] and 73% [19/26] by investigator review), respectively, in DLL3 \geq 50% tumors dosed at 0.2-0.4 mg/kg. Median overall survival (OS) was 7.7 months in DLL3 \geq 50% subjects at all dose levels, with a 1-year survival rate of 30%. In DLL3 \geq 50% tumors in the third line setting, rovalpituzumab tesirine achieved a 33% (4/12) and 83% (10/12) central review-adjudicated confirmed ORR and CBR, respectively, with a median survival of 5.8 months and a 1-year survival rate of 37%.

Rovalpituzumab tesirine was generally tolerated, with the most common Grade 3 or higher AEs of serosal effusions and thrombocytopenia occurring in 14% and 12% of subjects, respectively (AbbVie data on file). Therefore, rovalpituzumab tesirine appears to be an active anticancer therapy.

1.3 Immune Checkpoints and Inhibitors of PD-1 and CTLA-4

Immune checkpoint therapy targets regulatory pathways in T lymphocytes to enhance antitumor immune responses (Sharma, 2015). Agents inhibiting the interaction between programmed death receptor-1 (PD-1) and cytotoxic T-lymphocyte antigen 4 (CTLA-4) and their ligands have facilitated considerable progress in the treatment of many solid tumors: ipilimumab, a CTLA-4-blocking antibody, has been approved for the treatment of unresectable or metastatic melanoma (Bristol-Myers Squibb [BMS], 2015), while nivolumab, a PD-1 blocking antibody, has been approved for treatment as a single agent for metastatic NSCLC after platinum-based chemotherapy, advanced renal cell carcinoma (RCC) after prior anti-angiogenic therapy, and as a single agent or in combination with ipilimumab for unresectable or metastatic melanoma (BMS, 2016).

In an ongoing Phase 1/2 study, nivolumab with or without ipilimumab showed antitumor activity with durable responses and manageable safety profiles in previously treated patients with SCLC: nivolumab 3 mg/kg q2wk achieved a PR and SD in 10% (10/98) and 22% (22/98), respectively, while the combination of nivolumab and ipilimumab (1 and 1 mg/kg, 1 and 3 mg/kg, or 3 and 1 mg/kg, respectively) every 3 weeks (q3wk) x 4 followed by nivolumab 3 mg/kg q2wk achieved an ORR and SD in 23% (14/61) and 19% (10/54), respectively (Antonia, 2016). Treatment was generally well tolerated, with grade 3 or higher treatment-related AEs occurring in 13 (13%) patients in the nivolumab 3 mg/kg cohort, 18 (30%) in the nivolumab 1 mg/kg plus ipilimumab 3 mg/kg cohort, and 10 (19%) in the nivolumab 3 mg/kg plus ipilimumab 1 mg/kg cohort; the most commonly reported grade 3 or 4 treatment-related adverse events were increased lipase (none vs. 5 [8%] vs. none) and diarrhea (none vs. 3 [5%] vs. 1 [2%]). No patients in the nivolumab 1 mg/kg plus ipilimumab 1 mg/kg cohort had a grade 3 or 4 treatment-related adverse

event. Six (6%) patients in the nivolumab 3 mg/kg group, seven (11%) in the nivolumab 1 mg/kg plus ipilimumab 3 mg/kg group, and four (7%) in the nivolumab 3 mg/kg plus ipilimumab 1 mg/kg group discontinued treatment due to treatment-related adverse events. Two patients who received nivolumab 1 mg/kg plus ipilimumab 3 mg/kg died from treatment-related adverse events (myasthenia gravis and worsening of renal failure), and one patient who received nivolumab 3 mg/kg plus ipilimumab 1 mg/kg died from treatment-related pneumonitis. Nivolumab and the combination of nivolumab and ipilimumab, therefore, appear to have clinically significant therapeutic potential in SCLC (Antonia, 2016).

1.4 Rationale for the Study and Anticipated Risks

Although rovalpituzumab tesirine as well as the checkpoint inhibitors nivolumab and ipilimumab have demonstrated encouraging efficacy in SCLC, neither approach alone appears at this time sufficient to afford a complete clinical benefit or cure in the majority of patients, where medical need remains high. Their mechanisms of actions are complementary and toxicities generally non-overlapping, though, suggesting that combination therapy may be safe, and clinical benefit may be additive or even synergistic. Indeed, preliminary studies indicate that ADCs like rovalpituzumab tesirine may, at least in part, result in immunogenic cell death of tumors, complementing the immuno-regulatory effects of checkpoint inhibitors like nivolumab and/or ipilimumab (Gerber, 2016). However, no formal clinical studies have previously examined the tolerability of rovalpituzumab tesirine administered in combination with checkpoint inhibitors. This study will therefore explore the safety, tolerability, and antitumor activity of rovalpituzumab tesirine administered in combination with nivolumab with or without ipilimumab. Upon completion of the study, decisions to further advance this program will also include review of the ORR rate. The lower bound value of the 95% confidence interval for the ORR rate observed will be compared to the ORR rate of 23% and used as one of the factors in making the decision.

The most frequent treatment-emergent adverse event (TEAE) terms considered related to rovalpituzumab tesirine have included fatigue (35%), peripheral edema (23%), and nausea (19%), while the most frequent, related TEAEs of Grade 3 or higher have included serosal effusions (14%), thrombocytopenia (12%), and skin reactions (8%). In addition, preclinical toxicology studies conducted in the rat and the cynomolgus monkey have identified the bone marrow, lung and kidney as a potential source of clinical AEs (AbbVie data on file).

Warnings for nivolumab include immune-mediated reactions, including pneumonitis, colitis, hepatitis, endocrinopathies, nephritis, rash, and encephalitis, as well as infusion reactions and embryo-fetal toxicity. The most common adverse reactions ($\geq 20\%$) in patients with melanoma were fatigue, rash, musculoskeletal and back pain, pruritus, diarrhea, upper respiratory tract

infection, decreased appetite, and nausea as a single agent, and fatigue, rash, diarrhea, nausea, pyrexia, vomiting, and dyspnea when administered with ipilimumab. In metastatic non-small cell lung cancer (NSCLC), the most common adverse reactions ($\geq 20\%$) were fatigue, musculoskeletal pain, decreased appetite, cough, and constipation. In advanced renal RCC, they were asthenic conditions, cough, nausea, rash, dyspnea, diarrhea, constipation, decreased appetite, back pain, and arthralgia (BMS, 2016).

Warnings for ipilimumab also include immune-mediated reactions, including hepatitis and endocrinopathies, as well as embryo-fetal toxicity. The most common adverse reactions ($\geq 5\%$) have been fatigue, diarrhea, pruritus, rash, and colitis. At the 10 mg/kg dose (higher than anticipated in this study), additional common adverse reactions ($\geq 5\%$) include nausea, vomiting, headache, weight loss, pyrexia, decreased appetite, and insomnia (BMS, 2015).

Accordingly, safety assessments will include regular assessments at protocol-specified time points of routine physical examination, laboratory and imaging tests, as well as echocardiograms, a Fluid Retention Questionnaire, daily weights, and spot urine protein testing.

2. Objectives

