3.2 Discussion and Rationale for Study Design

3.2.1 Study Design

This is the first formal clinical study of rovalpituzumab tesirine in combination with an inhibitor of PD-1 and CTLA-4. Cohort 1 will first assess the tolerability of doublet rovalpituzumab tesirine and nivolumab, a PD-1 inhibitor; if tolerated, Cohort 2 will assess the tolerability of triplet rovalpituzumab tesirine, nivolumab, and ipilimumab; if tolerated, Cohort 3 will assess the tolerability of the triplet with a higher dose of ipilimumab. Expanded enrollment to each cohort may occur in order to explore further the tolerability of one or more regimen(s).

The evaluation of the study endpoints will inform the safety profile of rovalpituzumab tesirine in combination with nivolumab with or without ipilimumab, and may provide evidence of antitumor activity that could influence the trial design of subsequent studies in SCLC.

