3.2.3 Rationale for Selection of Doses

In a recent Phase 1 study with rovalpituzumab tesirine, the MTD was established at 0.4 mg/kg q3wk based on the incidence of Cycle 1 toxicities, while the recommended Phase 2 dose (RP2D) in SCLC was chosen as 0.3 mg/kg q6wk based on the toxicity and efficacy profile during multiple cycle dosing (AbbVie data on file).

In an ongoing Phase 1 study, nivolumab 3 mg/kg q2wk, and nivolumab 1 mg/kg + ipilimumab 3 mg/kg q3wk, were found to be tolerated in SCLC ([Antonia, 2015](#)). Since the toxicities of these therapies have been generally non-overlapping, the starting dose regimens in this study will therefore be rovalpituzumab tesirine 0.3 mg/kg q6wk + nivolumab 360 mg q3wk, rovalpituzumab tesirine 0.3 mg/kg q6wk + nivolumab 1 mg/kg q3wk + ipilimumab 1 mg/kg q3wk, and rovalpituzumab tesirine 0.3 mg/kg q6wk + nivolumab 1 mg/kg q3wk + ipilimumab 3 mg/kg q3wk. In all dose levels, nivolumab will be administered at 480 mg q4wk when used as a single agent or after 2 cycles at 360 mg in Cohort 1.

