3.2.5 Nivolumab Flat Dose Regimens

The safety and efficacy of 240 mg q2wk flat dose of nivolumab is similar to 3 mg/kg q2wk dosing regimen. A flat dose of nivolumab 240 mg q2wk was selected since it is identical to a dose of 3 mg/kg for subjects weighing 80 kg, the observed median body weight in nivolumab treated cancer patients. The 240 mg q2wk flat dose of nivolumab was recently approved by the FDA. Using a population pharmacokinetic (PPK) model, the overall distributions of nivolumab exposures (C_{avgss} , C_{minss} , C_{maxss} , and C_{min1}) are comparable after treatment with either 3 mg/kg or 240 mg nivolumab. The predicted range of nivolumab exposures (median and 90% prediction intervals) resulting from a 240 mg flat dose across the 35 to 160 kg weight range is maintained well below the corresponding exposures observed with the well tolerated 10 mg/kg nivolumab q2wk dosage. Across the various tumor types in the clinical program, nivolumab has been shown to be safe and well tolerated up to a dose level of 10 mg/kg, and the relationship between nivolumab exposure produced by 3 mg/kg and efficacy and safety has been found to be relatively flat. Given the similarity of nivolumab PK across tumor types and the similar exposures predicted following administration of 240 mg flat dose compared to 3 mg/kg q2wk regimen, it is expected that the safety and efficacy profile of 240 mg q2wk nivolumab will be similar to that of 3 mg/kg nivolumab.

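### Is a single ORR reference of 23% the wrong yardstick for Cohort 1, which receives no ipilimumab?

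*Combined protocol and SAP*

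**What the plan says.** Section 1.4 states that, once the study is complete, decisions to advance the program will also consider ORR: "The lower bound value of the 95% confidence interval for the ORR rate observed will be compared to the ORR rate of 23" per cent. The result is to be "used as one of the factors in making the decision". The section names no cohort and no source for the 23%.

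Section 1.3 holds the likely source. For nivolumab with ipilimumab it reports that treatment "achieved an ORR and SD in 23% (14/61) and 19% (10/54), respectively". For nivolumab alone it reports that "nivolumab 3 mg/kg q2wk achieved a PR and SD in 10% (10/98) and 22% (22/98), respectively".

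On the regimens, Section 3.2.1 says "Cohort 1 will first assess the tolerability of doublet rovalpituzumab tesirine and nivolumab, a PD-1 inhibitor"; ipilimumab enters only in Cohorts 2 and 3. Section 3.2.3 rests the starting regimens on two earlier ones: "nivolumab 3 mg/kg q2wk, and nivolumab 1 mg/kg + ipilimumab 3 mg/kg q3wk, were found to be tolerated in SCLC". Section 3.2.5 adds that "The safety and efficacy of 240 mg q2wk flat dose of nivolumab is similar to 3 mg/kg q2wk dosing regimen".

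Section 10.3.4 reports ORR with a 95% CI for each cohort and leaves the details to the SAP. Section 10.1 bases the sample size on safety and describes the efficacy evaluation, with 6 to 30 subjects per cohort, as preliminary. Section 2.2 makes efficacy a secondary objective, to be explored.

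**The concern.** A historical reference is usually matched to the regimen it judges. The 23% appears to come from nivolumab plus ipilimumab, whereas Cohort 1 gives nivolumab without ipilimumab. The protocol also holds a nivolumab-alone figure in the same disease, at a dose intensity it treats as comparable, and does not use it.

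Cohort 1 is the only cohort sure to open, since Cohort 2 depends on its tolerability. If escalation stopped there, the only ORR to set against 23% would come from a regimen without ipilimumab. A middling Cohort 1 result could then read as disappointing although its lower limit exceeds the nivolumab-alone rate. This is also the only numerical efficacy criterion in the document, and no minimum cohort size is attached to it.

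**Working it through.** **Inputs.** Nivolumab plus ipilimumab 14/61 and nivolumab alone 10/98 (Section 1.3); rovalpituzumab tesirine alone 8/26 by central review and 10/26 by investigator, in tumors with DLL3 of at least 50% (Section 1.2); up to about 30 subjects per cohort (Section 10.1). The protocol does not name the interval method, so I assume the exact (Clopper-Pearson) interval and give Wilson as a check.

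**The plan's figure.** 14/61 = 22.95%, which rounds to 23%. No other ORR in the document does. The sentence lists three dose pairs, but the safety counts point to one arm: "18 (30%) in the nivolumab 1 mg/kg plus ipilimumab 3 mg/kg cohort" fits a denominator of 60 or 61, and the 7 (11%) discontinuations in that arm need at least 61. So 14/61 looks like the nivolumab 1 mg/kg plus ipilimumab 3 mg/kg arm, whose checkpoint doses are those of Cohort 3.

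**The mismatch.** Nivolumab per week is 240/2 = 360/3 = 480/4 = 120 mg, so Cohort 1 matches the flat dose that Section 3.2.5 equates with 3 mg/kg q2wk. The exact 95% interval has lower limit Beta(0.025; x, n−x+1) and upper limit Beta(0.975; x+1, n−x):

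| Source | Rate | Exact 95% CI | Contains 23%? |
|---|---|---|---|
| Nivolumab alone, 10/98 | 10.2% | 5.0–18.0% | no |
| Nivolumab + ipilimumab, 14/61 | 23.0% | 13.1–35.5% | yes |
| Rovalpituzumab tesirine alone, 8/26 | 30.8% | 14.3–51.8% | yes |

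The 10/98 is labelled PR, so complete responses might be missing. Even 13/98 has an upper limit of 21.6%, so up to three more responders would not change the first row.

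**What the references require at n = 30.** The pass mark is the smallest number of responders whose lower limit exceeds the reference.

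- 23%: 13 responders (lower limit 25.5%; 12 gives 22.7%).
- 10/98: 8 responders (lower limit 12.3%; 7 gives 9.9%).

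Wilson intervals give 12 and 7. With exact intervals, results of 8 to 12 of 30 (27–40%) lie between the two marks. Binomial probabilities for assumed true ORRs:

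| True ORR | P(≥13) | P(≥8) | P(8–12) |
|---|---|---|---|
| 25% | 2% | 49% | 46% |
| 30% | 8% | 72% | 63% |
| 35% | 22% | 88% | 66% |
| 40% | 42% | 96% | 53% |

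The choice of reference therefore matters to how a Cohort 1 result would read.

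**Would 10% be the better reference?** Suppose nivolumab adds nothing to rovalpituzumab tesirine.

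- All 30 respond at 8/26: P(≥8) = 75% and P(8–12) = 65%.
- All 30 respond at 10/26: P(≥8) = 94%.
- Only up to the first 12 subjects per cohort must be DLL3 positive (Section 4.1). With 12 responding at 8/26 and 18 at an assumed 10%, 20% or 23%, P(≥8) = 16%, 45% or 54%.

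If instead rovalpituzumab tesirine adds nothing to nivolumab (true rate 10/98), P(≥8) = 0.9%. A 10% mark can thus show that the doublet beats nivolumab alone. It cannot show that the doublet is better than its more active component.

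**The case for a change.** The strongest case for a change accepts that 23% may be a deliberate common bar but asks the protocol to say so. It would show Cohort 1 against both 10% and 23%, so that 8 to 12 of 30 reads as above nivolumab alone and not as a miss. It would also print the pass marks, since at a true ORR of 30%, about three times the nivolumab-alone rate, Cohort 1 clears 23% only 8% of the time. Small cohorts should be descriptive, because 4/6 (lower limit 22.3%) and 6/12 (21.1%) both fall short.

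The arithmetic stands, and so does the observation that Section 1.4 gives neither source nor scope. The inference that Cohort 1 needs another benchmark does not. A reference for advancing a combination need not lie inside the interval of its weaker component; it is normally set above it. The 31% comes from a DLL3-selected group and may overstate what Cohort 1 would show, but that leaves the right reference open to judgement and does not make it 10%. Nor does the protocol contain a pass/fail rule under which 8 to 12 responders would fail. The interval method and any minimum cohort size are details of the kind that Section 10.3.4 leaves to the SAP, whose text is not available here.

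**Conclusion.** No change is needed. The single 23% does not match Cohort 1's checkpoint component, and its link to 14/61 is an inference, though a firm one. But 23% lies between the two single-agent rates for Cohort 1's drugs (10% and 31%), and asking a new doublet to do better than the stronger checkpoint result on file is a fair choice.

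The reference affects how 8 to 12 responders of 30 would read, assuming a full cohort of 30, exact intervals and a per-cohort reading of Section 1.4. That reading feeds a sponsor judgement with several inputs. It does not affect any subject, dose, sample size or planned analysis. Since each cohort's ORR and interval are reported, anyone weighing Cohort 1 can set its result beside 10/98, 14/61 and 8/26, all of which are already in Sections 1.2 and 1.3. Stating the source of 23% would help the reader but would not alter the plan.

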4.1 Inclusion Criteria

- 1) Written informed consent.
 - a) Must have signed and dated an IRB/IEC approved written informed consent form (ICF) in accordance with regulatory and institutional guidelines. This must be obtained before the performance of any protocol-related procedures that are not part of normal patient care.
 - b) Must be willing and able to comply with scheduled visits, treatment schedule, laboratory testing, and other requirements of the study.
- 2) Target population
 - a) Histologically or cytologically confirmed extensive-stage SCLC with PD after at least one platinum-based chemotherapeutic regimen.
 - b) Measurable disease, defined as at least 1 tumor lesion ≥ 10 mm in the longest diameter or a lymph node ≥ 15 mm in short-axis measurement assessed by computerized tomography (CT) scan (RECIST v1.1) or evaluable disease.
 - c) Availability of representative baseline tumor tissue (archived or on-study biopsy) suitable for immunohistochemistry testing. Up to the first 12 subjects of each study cohort must be DLL3 positive per IHC (Immunohistochemistry) assay criteria, based on central assessment prior to enrollment.
 - d) ECOG performance status of 0 or 1. See Appendix 13.3 for conversion of performance status using Karnofsky scales, if applicable.
 - e) Minimum life expectancy of at least 12 weeks.

- f) Asymptomatic central nervous system (CNS) metastases, if present, must be stable, with or without previous treatment, in the absence of corticosteroids for at least 2 weeks prior to initiation of study drugs.
 - g) Recovery to Grade 1 of any clinically significant toxicity (excluding alopecia) prior to initiation of administration of study drugs.
 - h) Satisfactory laboratory parameters:
 - i. Absolute neutrophil count (ANC) $\geq 1,000/\mu\text{L}$.
 - ii. White blood cell count (WBC) $\geq 2,500/\mu\text{L}$.
 - iii. Platelet count $\geq 100,000/\mu\text{L}$.
 - iv. Hemoglobin ≥ 9.0 g/dL.
 - v. Total bilirubin ≤ 1.5 x upper limit of normal (ULN) or ≤ 3 x ULN for subjects with Gilbert's disease.
 - vi. Alanine aminotransferase (ALT) and aspartate aminotransferase (AST) ≤ 3.0 x ULN (≤ 5 x ULN if evidence of hepatic involvement by malignant disease).
 - vii. Creatinine ≤ 1.5 x ULN or estimated glomerular filtration rate (eGFR) ≥ 40 mL/min/1.73m².
 - viii. Albumin ≥ 3 g/dL.
 - iv. Lipase ≤ 1.5 x ULN. Subjects with Lipase > 1.5 x ULN may enroll if there are neither clinical nor radiographic signs of a pancreatitis.

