6.3 Screening Visit (Days -14 to -1)

Informed consent for the main portion of this study will be obtained prior to the performance of any study procedures and may occur within 30 days prior to the Day 1 Visit. All other screening procedures must occur within 14 days prior to Day 1. Imaging performed as standard of care within 14 days prior to Day 1 will be accepted.

The following assessments will occur during Screening:

- Informed consent – omitted for retreatment subjects

- Demographics (Section 7.1) – omitted for retreatment subjects
- Confirmation of study eligibility per inclusion/exclusion criteria (Section 4); if prescreening visit was not conducted, testing of an archived or fresh tumor tissue specimen for DLL3 expression will be conducted during the Screening Visit. Upon enrollment into the study, remaining tumor tissue will be analyzed for PD-L1 expression.
- Medical and surgical history (Section 7.1) – omitted for retreatment subjects
- Malignancy history (Section 7.1) – omitted for retreatment subjects
- Prior anticancer treatments (Section 7.1) – omitted for retreatment subjects
- Physical examination (Section 7.7.1)
- Vital signs (Section 7.7.2)
- Height (Section 7.7.2) (For adult subjects (≥ 18 years), measurements of height obtained within 6 months prior to Screening Visit may be utilized)
- Urinalysis (Section 7.7.3)
- Triplicate electrocardiogram (ECG)
- ECOG performance status (Section 7.7.6 and Appendix 13.3)
- Procedure-related AEs (Section 7.6)
- Procedure-related concomitant medications
- Disease assessment consisting of CT scans of the chest, abdomen, and pelvis (and neck if indicated) (Section 7.2) – may be omitted for all subjects if recent scans demonstrating PD are within 14 days prior to dosing of study drugs.
- Magnetic resonance imaging (MRI) of the brain – may be omitted for all subjects if recent scans are taken within 14 days prior to dosing of study drugs. CT of the brain with IV contrast may be substituted at the discretion of the investigator. (Section 7.2)
- Paraneoplastic Assessment (Appendix 13.8)
- Blood sample collection for:
 - Complete blood count (CBC) with differential (Section 7.7.3)
 - Serum chemistries (Section 7.7.3)
 - Coagulation tests (Section 7.7.3)
 - Hepatitis B and C tests (Section 7.7.3) – omitted for retreatment subjects
 - Pregnancy test (serum) (Section 7.7.3) for women of child-bearing potential

- Blood ██████████ (Section 7.4.2)
- Blood soluble markers (Section 7.4.3)

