7.2.2 Central Radiographic Assessment

Radiological scans will be collected for assessment by a Central Radiographic Assessment Reader. Within 24 hours of each subject's disease assessment, the appropriate scans should be sent by overnight courier or electronically to the central facility. The central reader will make the definitive decision on tumor burden (including measurable disease) and tumor response, which will be relayed to the investigator. All decisions on treatment eligibility, continuation, discontinuation, and retreatment will be made based on the tumor response adjudicated by the central reader.

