10.1 Determination of Sample Size

Up to approximately 90 subjects are expected to participate in this three-cohort trial (up to approximately 30 per cohort).

The primary objective of this study is to determine the tolerability, adverse event profile, and any DLTs for rovalpituzumab tesirine when given in combination with nivolumab or nivolumab and ipilimumab intravenously in adult subjects with extensive-stage small cell lung cancer. Safety will be monitored throughout the trial by the safety monitoring committee (SMC). The sample size for this study is based on the need to establish safety of the regimens being evaluated and 6 subjects is the minimum number required for the clinical safety evaluation of each cohort and 12 subjects may need to be enrolled in order to evaluate safety after 12 weeks in at least 6 subjects. Enrollment of a minimum of 6 subjects and a maximum of 30 subjects per cohort will allow for a preliminary evaluation of efficacy.

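### Does the 23% ORR reference in Section 1.4 need a companion reference for rovalpituzumab tesirine alone?

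*Combined protocol and SAP*

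**What the plan says.** Section 1.4 holds the only numerical efficacy criterion in the protocol: "The lower bound value of the 95% confidence interval for the ORR rate observed will be compared to the ORR rate of 23" per cent. The same sentence makes this one of several factors in the decision, and gives no source for the figure.

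Two background sections bear on it:

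- Section 1.3 says that nivolumab plus ipilimumab, listed at three dose pairs, "achieved an ORR and SD in 23% (14/61) and 19% (10/54), respectively". For nivolumab alone it gives a partial response rate of 10% (10/98).
- Section 1.2 gives rovalpituzumab tesirine alone, in DLL3 ≥50% tumors dosed at 0.2–0.4 mg/kg, a confirmed ORR of 31% (8/26) by central review and 39% (10/26) by investigator review.

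On who is enrolled and how response is read, Section 4.1 states that "Up to the first 12 subjects of each study cohort must be DLL3 positive per IHC" assay criteria, with no numerical cut-off. Section 7.2.2 states that "The central reader will make the definitive decision on tumor burden (including measurable disease) and tumor response". Section 10.3.4 gives the ORR and its 95% CI for each cohort and leaves further detail to the SAP. Section 10.1 bases the sample size on safety and adds only that "Enrollment of a minimum of 6 subjects and a maximum of 30 subjects per cohort will allow for a preliminary evaluation of efficacy".

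**The concern.** Section 1.4 motivates the combination by suggesting that the two mechanisms may add to or reinforce one another. Its one numerical comparison, however, appears to use a rate for the checkpoint drugs by themselves. If subjects with high DLL3 expression respond to rovalpituzumab tesirine alone about 31% of the time, a cohort in which nivolumab and ipilimumab contribute nothing could still clear 23%. A reader might take that as evidence that the combination works better than its parts, and a later study could be built on it.

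The provenance of 23% adds to the unease. Section 1.3 presents 14/61 and 10/54 as two outcomes of one pooled group, yet the denominators differ. The CI method, which moves the pass mark, is not named.

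**Working it through.** **1. Where 23% comes from.** 14/61 = 22.95%, which rounds to 23%. No other ORR in the document does. Section 1.3 also gives adverse-event counts by arm, and these identify the denominators:

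| Arm | Count = printed % | Denominators that fit | Common value |
|---|---|---|---|
| Nivolumab 1 + ipilimumab 3 mg/kg | 18 = 30% | 60, 61 | |
| | 7 = 11% | 61 to 66 | **61** |
| Nivolumab 3 + ipilimumab 1 mg/kg | 10 = 19% | 52 to 54 | |
| | 4 = 7% | 54 to 61 | **54** |

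The counts of 7 and 4 are those in "seven (11%) in the nivolumab 1 mg/kg plus ipilimumab 3 mg/kg group, and four (7%) in the nivolumab 3 mg/kg" plus ipilimumab 1 mg/kg. So the ORR of 14/61 and the SD rate of 10/54 come from different arms, and 23% describes one regimen. By checkpoint doses that regimen matches only Cohort 3 (Section 3.1, Table 1): Cohort 2 uses ipilimumab 1 mg/kg and Cohort 1 has no ipilimumab.

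**2. What a pass requires.** Take n = 30, the cohort maximum, and find the smallest number of responders r whose two-sided 95% lower bound exceeds 23%.

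- Exact (Clopper-Pearson): 12/30 gives 22.7% (fails); 13/30 gives 25.5% (passes). Observed rate 13/30 = 43.3%.
- Wilson: 12/30 gives 24.6% (passes). Observed rate 12/30 = 40.0%.

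Both observed rates exceed the single-agent estimates, 8/26 = 30.8% and 10/26 = 38.5% (printed as 39%). Exceeding an estimate is not excluding it: at 13/30 and 14/30 the exact lower bounds, 25.5% and 28.3%, are still below 31%.

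**3. How often a regimen that adds nothing passes.** P(X ≥ r) for X ~ Binomial(30, p):

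| True ORR p | Exact, r = 13 | Wilson, r = 12 |
|---|---|---|
| 23% | 1.1% | 2.8% |
| 25% (assumed mixed cohort) | 2.2% | 5.1% |
| 27% (assumed mixed cohort) | 3.9% | 8.4% |
| 31% (all DLL3-high, central read) | 10.5% | 19.1% |
| 39% (all DLL3-high, investigator read) | 37.8% | 52.4% |

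The last two rows need all 30 subjects to be DLL3 ≥50%, which the protocol does not require. The 25–27% range is an assumption, since the document gives no rate for a mixed cohort. At n = 12 and p = 31% the chance is 4.6% (exact, 7/12 needed) or 13.4% (Wilson, 6/12 needed).

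**4. How firm the alternative reference is.** The exact 95% CI for 8/26 is 14.3–51.8%, and for 14/61 it is 13.2–35.5%. The first contains 23% and the second contains 31%, so the document does not establish that 23% lies below the single-agent rate in this trial's population. The 8/26 also pools 0.2–0.4 mg/kg, whereas this trial plans 0.3 mg/kg.

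**5. What a 31% reference would deliver.** A lower bound above 31% needs 15/30 (exact, 31.3%). At a true ORR of 50% that is reached 57.2% of the time, against 81.9% for the 23% bar. In a DLL3-high subset of 12 it needs 8/12 (exact), reached 19.4% of the time at a true 50%.

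**The case for a change.** The case for a change is that the rule has no reference for the one drug every subject receives, and that the choices left open matter. In cohorts made up entirely of DLL3-high subjects, 10.5% is well above 1.1%. Taking three such cohorts of 30 as independent, the chance that at least one passes is 1 − (1 − 0.105)³ ≈ 28%. Moving from an exact to a Wilson interval nearly doubles the single-cohort figure. If the rule were applied to all 90 subjects pooled, 30/90 would suffice (exact), and the chance at a true 31% would be 35.3%. DLL3 testing and central reads are already planned, so a DLL3-high table and a line on interpretation would cost little.

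The arithmetic stands, and so does the point that clearing 23% is not evidence of benefit over rovalpituzumab tesirine alone. The rest carries less weight:

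- The protocol does not make that inference. The additive or synergistic language is a tentative rationale, and Section 3.2.1 promises only possible evidence of antitumor activity to inform later designs.
- No fixed threshold in a single-arm cohort can isolate one component's contribution, whether it is set at 23% or 31%.
- Pooling is not what Section 10.3.4 describes; it reports ORR by cohort.
- Section 2.3 already makes the relation between DLL3 expression and outcome an exploratory objective, and Section 10.3.6 allows it to be examined against response. A table beside 8/26 would alter no rule or result, and would invite comparison with a small, selected, dose-pooled series.

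**Conclusion.** No change to the plan follows. The 23% bar is a modest reference for activity, used as one input to a development decision in a study whose primary objective and sample size rest on safety. It is a fair trade-off: it already demands an observed ORR of 40–43% at 30 subjects, and a 31% reference would be stricter without being better founded.

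The source of 23%, the interval method, the reader and the unit of analysis are details that the SAP or the analysts would settle sensibly. Section 10.3.4 points to per-cohort intervals, Section 7.2 to confirmed responses, and Section 7.2.2 to the central read, although Section 7.2 also mentions the investigator's determination. The mixed-arm sentence in Section 1.3 is a clerical slip in background text and leaves the rule as it is.

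The size of the issue is a 2–4% (exact) or 5–8% (Wilson) chance that a mixed cohort of 30 passes with no checkpoint contribution, rising to 10.5% or 19.1% if every subject is DLL3-high with a true rate of 31%, and higher still if the 39% investigator rate applies. This rests on three things: reading 14/61 as the source of 23%, which is inferred; the assumed 25–27% for a mixed cohort; and full enrolment of 30. The conclusion would differ if a report presented a pass at 23% as proof that the combination adds to rovalpituzumab tesirine alone; nothing in the protocol plans that.
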